6.7.3 Visit 3 (Day 0): AMDC Injection Procedure

[REDACTED] after the muscle biopsy, patients will return to the clinic for a brief outpatient procedure. Prior to injection, if appropriate, patients will also have a urine sample collected for pregnancy testing. Patients will also have their temperature measured and be assessed for signs of infection and changes in anorectal condition that may affect the "At Time of Cell Delivery" exclusion criteria. After confirming eligibility, the AMDC product will be prepared and injected into the external anal sphincter in accordance with instructions for use (as described in Section 3.3). Post-injection, injection sites will be inspected for the presence of bleeding or excessive trauma.

The medication log will be updated if necessary and adverse events will be recorded and reported as appropriate. Patients will be reminded not to change (to the greatest degree possible) their medication regimen, and other coping mechanisms, related to their fecal incontinence condition. Patients will be given a 28-day diary to report fecal incontinence data. The diary should be completed during the 28 days leading up to, and returned to the site at, the next scheduled visit (3 Month Follow-up Visit).

6.7.4 Phone Contact (Day 1 to 2): Post-treatment Follow-up

Between 24 and 48 hours after treatment, patients will be contacted by phone to determine if any adverse events have occurred and if the patient has any updates for the medication log.

6.7.5 Phone Contact (Month 1, ± 1 week): Post-treatment Follow-up

One month after the AMDC injection procedure the patients will be contacted by phone to determine if any adverse events have occurred and if the patients have any updates for the medication log.

6.7.6 Visit 4 (Month 3, ± 1 week): Post-treatment Follow-up

Patients will return to the clinic for evaluation. A physical examination (clinical assessment), including a visual inspection, digital rectal examination, and anoscopy and/or sigmoidoscopy (at

physician's discretion), will be performed. During the visit, the patient will complete the FIQL and Wexner score questionnaires (administered by a member of the research staff). The medication log will be updated if necessary and adverse events will be recorded and reported as appropriate.

Patients will return their recently completed 28-day diary and will be given another 28-day diary to report fecal incontinence data. The diary should be completed during the 28-days leading up to, and returned to the site at, the next scheduled visit (6 Month Follow-up Visit). Patients may be contacted as a reminder when to start the diary.

6.7.7 Visit 5 (Month 6, -2, +4 weeks): Post-treatment Follow-up

Patients will return to the clinic for evaluation. A physical examination (clinical assessment), including a visual inspection, digital rectal examination, and anoscopy and/or sigmoidoscopy (at physician's discretion), will be performed. During the visit, the patient will complete the FIQL and Wexner score questionnaires (administered by a member of the research staff). The medication log will be updated if necessary and adverse events will be recorded and reported as appropriate.

Patients will return their recently completed 28-day diary and will be given another 28-day diary to report fecal incontinence data. The diary should be completed during the 28-days leading up to, and returned to the site at, the next scheduled visit (12 Month Follow-up Visit). Patients may be contacted as a reminder when to start the diary.

6.7.8 Visit 6 (Month 12, -2, +4 weeks): Post-treatment Follow-up

Patients will return to the clinic for evaluation. A physical examination (clinical assessment), including a visual inspection, digital rectal examination, and anoscopy and/or sigmoidoscopy (at physician's discretion), will be performed. During the visit, the patient will complete the FIQL and Wexner score questionnaires (administered by a member of the research staff). The medication log will be updated if necessary and adverse events will be recorded and reported as appropriate. Patients will return their recently completed 28-day diary. Additionally, an endoanal ultrasound and an anorectal manometry evaluation will be performed.

After completing the 12 month follow-up, patients will be considered as having completed the study.

6.8 Criteria and Procedures for Withdrawal

A patient may decide to withdraw from the investigation at any time without prejudice or loss of care. An effort will be made to obtain, in writing, notification from patient of desire to withdraw. The Investigator may also decide to withdraw the patient from the investigation at any time based on medical judgment. In these instances, the appropriate case report forms and study exit form must be completed. The reason why the patient has withdrawn shall be stated on the study exit form.

If a patient should discontinue the study for any reason, a study exit form will be completed. On this form, the reason for discontinuation will be indicated (e.g. death, lost to follow-up, withdrawal, or completion of study). Space is also provided for documentation of further explanation of discontinuation.

In the event a patient is lost to follow-up or fails to appear for scheduled post-treatment assessment, efforts will be made to locate the patient before filing a study exit form, and these efforts will be documented.

If a patient receives treatment other than the study procedure (e.g. receives an injection of a bulking agent, or completes a surgery) before the completion of all scheduled follow-ups, then the patient will be withdrawn from the study and follow-up will be terminated. In this event, an attempt to collect safety and effectiveness measures prior to additional procedures will be made. The patient will be considered withdrawn on the study exit form.

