1.0 Clinical Investigation Plan Overview

This study is designed to test the safety and feasibility of Autologous Muscle Derived Cells (AMDC) as a treatment for fecal incontinence in men and women. AMDC therapy seeks to allow remodeling of the external anal sphincter in patients with fecal incontinence from either defined structural defects to, or a generalized weakening of, the external anal sphincter. This treatment is hypothesized to reduce symptoms of fecal incontinence and improve patient quality of life by strengthening the external anal sphincter muscle. The study will treat a total of 50 patients with 250×10^6 cells each.

The primary objective is to determine the incidence of product- or procedure-related adverse events associated with the use of AMDC. Patients will be followed for 12 months.

All eligible patients consenting to study participation will have skeletal muscle tissue harvested using a needle biopsy during an initial outpatient procedure. The harvested muscle tissue will be placed in a hypothermic medium and transported to the manufacturer for processing in their cell processing facility in Pittsburgh, Pennsylvania, USA. The AMDC will be isolated and expanded in culture over several weeks to the final dose of 250×10^6 cells.

After reaching the desired concentration, the isolated and expanded cell population of AMDC will be quality tested and then cryopreserved and shipped back to the investigating physician. The physician will thaw and dilute the cells with saline. The resulting suspension will be injected into the patient's external anal sphincter in a brief outpatient procedure using a small needle under direct vision. Endoanal ultrasound may be used, at the physician's discretion to visualize the location of the injection needle within the external anal sphincter.

A detailed description of the study flow is illustrated in Appendix A.

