2.0 Objectives of the Clinical Investigation

2.1 Primary Objective

The primary objective is to determine the incidence of product- or procedure-related adverse events associated with the use of AMDC within 12 months post-treatment.

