5.2 Methods to Minimize Risks

The procedure for proper deployment of the product at the intended site is described in the Summary Description of Procedures and the Instructions for Use (Sections 3.3.1 and 3.3.2). Only qualified physicians experienced in performing anorectal procedures will inject the product. Appropriate patient selection and adherence to and training on the research protocol are necessary to reduce product- and procedure-related risk. Routine venipuncture will be performed by qualified personnel.

Injection of AMDC will occur under direct vision. The presence of bleeding or puncture will be ascertained following injection. In addition, this investigation includes a high level of monitoring. The risks of continued incontinence, infection, and allergic reaction to the injected reagents will be assessed through patient report, a patient fecal incontinence diary that will be kept at various time points throughout the study, and clinical follow-up at 3, 6, and 12 months after treatment. Patients will be contacted by phone 24-48 hours and one month after injection to assess for adverse events.

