6.10 Safety Monitoring and Reporting of Adverse Events

A Data Safety Monitoring Board (DSMB) consisting of independent physicians, who are not investigators in the study, nor have a perceived conflict of interest with the conduct and administration of the investigation, may be convened to evaluate investigation progress and review adverse events.

An independent Clinical Events Committee (CEC) consisting of physicians, who are not investigators in the study, nor have a perceived conflict of interest with the conduct and administration of the study, may be established to adjudicate clinical events reported during the study. This adjudication will be performed according to standard operating procedures to assess whether the events were due to a pre-existing or unrelated condition, procedure-related, technique-related, and/or product-related.

Regularly scheduled monitoring, including on-site visits, will be conducted, in part, for identification of adverse events and assurance that they are accurately reported within the appropriate time frame.

Definitions for adverse events were derived from the ICH guideline on Clinical Data Safety Management: Definitions and Standards for Expedited Reporting, Section II: Definitions and

Terminology Associated with Clinical Safety Experience. Definitions are provided in Appendix D.

All adverse events (or adverse experiences), related or unrelated to the AMDC product or procedure, should be reported on the Event case report form within ten days of the site's knowledge of the adverse event.

All serious adverse events, serious adverse drug reactions, and suspected unexpected serious adverse drug reactions (SUSARs) related to the AMDC product or procedure shall be reported immediately to the data coordinating center (Cook Research Incorporated), who will inform the Sponsor accordingly. The immediate report should be made by the investigator within a very short period of time and under no circumstances should this exceed 24 hours following knowledge of the serious adverse event. SUSARs that are life-threatening or have been lethal will be reported, at the latest, within 7 days after the Sponsor becomes aware of them. All relevant information about the aftermath of this will be reported within a time period of another 8 days. Other reports of SUSARs will be made within 15 days after the Sponsor becomes aware of them.

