8.0 Deviations from Clinical Investigation Plan

Deviations or non-compliances will be recorded together with an explanation. Deviations that impact the rights, welfare or safety of patients shall be reported to the sponsor, regulatory authorities and Ethics Committee/REB as required.

The reasons for withdrawal and discontinuation of any patient from the study should be recorded, if possible. If such discontinuation is because of problems with safety or lack of effectiveness, that patient should still be followed-up in the study, if possible.

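### Sections 6.8 and 8.0 give opposite follow-up rules for a patient who has other treatment after AMDC fails or causes harm, so part of the 12-month safety window can be lost

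*Combined protocol and SAP*

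**What the plan says.** The primary objective in Section 2.1 is the "incidence of product- or procedure-related adverse events associated with the use of AMDC within 12 months post-treatment". The overview in Section 1.0 states "Patients will be followed for 12 months", and Section 5.2 relies on "clinical follow-up at 3, 6, and 12 months after treatment" as one of its means of assessing risk.

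Two sections then deal with patients who leave early:

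- **Section 6.8** applies when a patient receives "treatment other than the study procedure (e.g. receives an injection of a bulking agent, or completes a surgery" before all scheduled follow-ups are complete; "then the patient will be withdrawn from the study and follow-up will be terminated". The only mitigation is that "an attempt to collect safety and effectiveness measures prior to additional procedures will be made".
- **Section 8.0** covers withdrawal and discontinuation of any patient: "If such discontinuation is because of problems with safety or lack of effectiveness, that patient should still be followed-up in the study, if possible".

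Section 6.10 requires all adverse events, related or not, to be reported; they "should be reported on the Event case report form within ten days of the site's knowledge of the adverse event". Section 7.2 is a short descriptive plan. It names no denominator for the primary incidence and has no rule for patients with less than 12 months of follow-up.

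**The concern.** Patients who seek another procedure after AMDC are likely to be those in whom it did not work or caused a problem. These are the patients whom Section 8.0 wants to keep under observation and whom Section 6.8 removes from it. With no order of precedence, sites may handle the same case differently, and the length of safety observation then depends on outcome and on site.

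The trigger is also loosely drawn. The two examples in 6.8 do not settle whether treatment unrelated to incontinence, such as an unrelated operation, ends follow-up.

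The stake is the primary objective. A patient who leaves because of a related event is already in the numerator, so patient-level incidence does not change. For a patient who leaves without one, typically for lack of effect, a first related event after exit may never be recorded.

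**Working it through.** **Text comparison.** Take a patient treated with AMDC who has no benefit and receives a bulking-agent injection after the Month 3 visit.

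1. Section 6.8 applies because other treatment was given before follow-up was complete. The patient is withdrawn and follow-up ends.
2. Section 8.0 applies because its scope is any patient and the reason is lack of effectiveness. Follow-up should continue if possible.
3. No passage ranks the two sections.
4. Section 6.10 does not close the gap. Its reporting clock starts when the site learns of an event, and after exit no scheduled contact remains through which it would learn of one.
5. Section 9.0 does not close it either. Its statement that included cases stay in the analysed population concerns a centre that stops enrolling after disagreeing with a DSMB decision. Keeping a case in the analysis also does not recover unobserved months.

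**What follows from the documents.** The inputs are 50 treated patients (Sections 1.0, 6.1 and 6.6), a 12-month window (Section 2.1), and clinic visits at Months 3, 6 and 12 (Section 6.7).

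- Planned observation: 50 × 12 = 600 patient-months.
- Exit just after Month 3 loses 9 of 12 months and two clinic visits. Exit just after Month 6 loses 6 months and one visit.
- Each patient who exits without a related event leaves 1/50 = 2.0 points undetermined. Five such patients leave 10 points and fifteen leave 30 points. These are outer bounds, not expected shifts.

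**Illustration.** The documents give no rate of other treatment and no event rate, so everything from here rests on assumptions. Let L = 5, 10 or 15 patients leave, with exit uniform over Months 3 to 12 (mean loss 4.5 months).

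- Time lost: L × 4.5 = 22.5, 45 and 67.5 patient-months, or 3.75%, 7.5% and 11.25% of 600.
- Missed first events: let the risk over the last 9 months be q = 0.10 for a patient event-free at Month 3, with constant hazard h = −ln(0.9)/9. For exit at u months after Month 3, the chance of a missed first event is exp(−hu) − exp(−9h). Averaged over u from 0 to 9 this is 0.1/0.10536 − 0.9 = 0.0491 per leaver.
- With a share f of leavers whose related event is already counted, missed events = L(1 − f) × 0.0491:

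| f | L = 5 | L = 10 | L = 15 |
|---|---|---|---|
| 0 | 0.246 (0.49 points) | 0.491 (0.98) | 0.737 (1.47) |
| 0.5 | 0.123 (0.25) | 0.246 (0.49) | 0.368 (0.74) |
| 1 | 0 | 0 | 0 |

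- At q = 0.05 the per-leaver figure is 0.0248. With f = 0 this gives 0.12 to 0.37 events (0.25 to 0.74 points).

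**Harsher exit pattern.** Let a fraction g of patients all exit at month m, with true 12-month incidence p, h = −ln(1 − p)/12, and leavers at the same risk as everyone else. The crude incidence over 50 is (1 − g)p + g(1 − exp(−hm)). For g from 10% to 30% and m = 3, 6 or 9, 15 to 135 of 600 patient-months are lost (2.5% to 22.5%). A true 10% would read 7.8% to 9.8%, a true 20% would read 15.6% to 19.5%, and a true 30% would read 23.6% to 29.4%.

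**Error in the other direction.** Appendix D treats a reaction as related unless the link can be excluded, so an event due to the second procedure could be attributed to AMDC. If that happened in 10% of event-free leavers, 0.5 to 1.5 events (1.0 to 3.0 points) would be added at f = 0, and 0.25 to 0.75 events (0.5 to 1.5 points) at f = 0.5.

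**Scale.** With full follow-up, 5/50 has an exact (Clopper-Pearson) 95% interval of 3.3% to 21.8%.

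**The case against.** The best defence is that 6.8 is a specific, mandatory rule for one trigger, while 8.0 is a general, qualified statement under a heading about deviations, so 6.8 can be read as the exception. That reading is reasonable, but the documents do not state it. It also leaves the problem in place, because the follow-up that 8.0 asks for would then be barred wherever the two overlap.

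Stopping observation after a second procedure also has a rationale, since attribution becomes harder. On equal 10% assumptions the possible over-count (1.0 to 3.0 points) is about twice the under-count (0.5 to 1.5 points). This stands as a reason to separate events before and after the second procedure. It is not a reason to stop looking.

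Other points stand in part:

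- Sections 1.0 and 5.2 describe the planned schedule, which any withdrawal shortens. They show what is lost but are not a separate contradiction.
- Section 6.8 goes on to speak of additional procedures, and Section 6.7 allows medication under standard of care. Routine medication is therefore probably not a trigger, but unrelated surgery remains unclear.
- Section 7.1 speaks of 50 enrolled, and Section 6.5 places enrolment at biopsy, so the treated number could be below 50. The 2.0-point figure uses the 50 treated stated in three other sections.
- Scheduled visits include anorectal examination. The case for continued follow-up concerns adverse-event collection only.
- Section 6.9 already says the study is too small to establish safety. It also says the study should indicate safety and inform a larger trial, which is a reason to want the safety record complete.

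**Conclusion.** The concern holds. For patients who have other treatment because of AMDC failure or harm, the two sections give incompatible instructions. Following 6.8 ends observation inside the primary safety window for patients who do not leave at random. The text comparison is firm; the size of the effect is not known.

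The 2.0 points per event-free early exit assumes only that 50 are treated. Under the main illustration the expected understatement is 0.5 to 1.5 points, falling to zero if every leaver already has a counted event. It reaches 2.2 points for a true incidence of 10%, and 6.4 points for a true 30%, only if 30% of patients all leave at Month 3. For an incidence near 10% the shift is small against the sampling uncertainty. The analysis is descriptive, so no test decision is at risk. What is lost is completeness of the safety description, which is the study's main product, and the gap can be closed by rewording. It should be fixed.

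**What to change.** - **Sections 6.8 and 8.0:** reconcile them into one data-collection rule. When a treated patient receives other treatment, record it and, unless consent is withdrawn, continue adverse-event collection at the time points already scheduled to Month 12. State which other treatments trigger the rule.
- **Section 7.2:** report the primary incidence over all treated patients, show events before and after other treatment separately, and give the number who exited before Month 12 without a related event. Report effectiveness, ultrasound and manometry data obtained after other treatment separately, and state how many patients lack 12-month values for this reason. Imputation analyses are optional.

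This changes what is observed and reported, not which treatments a patient may receive. The cost is wording in three sections plus adverse-event collection for the few patients who would otherwise have exited; the contacts are already scheduled. Attribution after a second procedure will be less certain, and the before/after split keeps that visible.

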2.2 Secondary Objectives

The secondary objectives are to study the effect of AMDC treatment for fecal incontinence on:

- Changes from baseline in the frequency and nature of incontinent episodes at 3, 6, and 12 months post-treatment as measured by a patient fecal incontinence diary

- Changes from baseline in Wexner incontinence score [1] (copy provided in Appendix B) at 3, 6, and 12 months post-treatment
- Changes from baseline in Fecal Incontinence Quality of Life Scale (FIQL) [2] (copy provided in Appendix C) scores at 3, 6, and 12 months post-treatment
- Changes from baseline in sphincter function as measured by anorectal manometry at 12 months
- Changes from baseline in sphincter morphology as measured by endoanal ultrasound at 12 months
- Safety as measured by adverse events

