7.2 Analysis Plan

Endpoints will be summarized using frequency tables, means and standard deviations, 95% confidence intervals, and/or medians and ranges. Although it is expected that the study will

have too few patients, exploratory analyses of subgroups and covariates may be performed to investigate their relationship to AMDC treatment and to generate hypothesis and pilot data for future larger studies.

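### Patients who receive another treatment leave the later efficacy summaries, no endpoint or analysis rule counts them, and sections 6.8 and 8.0 conflict on whether they are followed

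*Combined protocol and SAP*

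**What the plan says.** Section 6.8 covers patients who receive a treatment other than the study procedure before their scheduled follow-up is complete; its examples are a bulking-agent injection and surgery. In that case, "then the patient will be withdrawn from the study and follow-up will be terminated". The section adds that "an attempt to collect safety and effectiveness measures prior to additional procedures will be made". The patient is recorded as withdrawn on the study exit form, where the reason for withdrawal must be given.

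Section 8.0 deals with discontinuation because of safety problems or lack of effectiveness, and says "that patient should still be followed-up in the study, if possible".

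The efficacy objectives in 2.2 are all changes from baseline at fixed times. They include "Changes from baseline in the frequency and nature of incontinent episodes at 3, 6, and 12 months post-treatment" and "Changes from baseline in Wexner incontinence score" at the same three visits, with FIQL on that schedule too. Manometry and endoanal ultrasound are assessed after treatment at 12 months only.

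The analysis text in 7.2 is: "Endpoints will be summarized using frequency tables, means and standard deviations, 95% confidence intervals, and/or medians and ranges". Exploratory subgroup and covariate analyses may follow. The section names no analysis set, gives no missing-data rule and does not mention patients who received another treatment.

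**The concern.** A move to a bulking agent or surgery for incontinence is likely to reflect an unsatisfactory result of AMDC. Under 6.8 its only effect on the efficacy data is to remove the patient from later visits, because none of the objectives in 2.2 registers it as an outcome. The scores that 6.8 tries to obtain beforehand fall at an unscheduled time, and 7.2 gives them no place in the 3-, 6- or 12-month change.

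If the values that happen to be available are then averaged, the loss is related to outcome and the remaining mean tends to look better than the mean over everyone treated. Losses accumulate with time, so 12 months is the most exposed visit, and it is the only one for manometry and ultrasound. The study has no control arm in which the same distortion could be seen. Section 7.1 says the sample can show potential efficacy, and 6.9 says the results may inform a larger trial, so the 12-month change is a figure likely to be carried forward.

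**Working it through.** **Reading the sections together.** Take a patient whose AMDC result is poor and who has surgery at month 4.

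- Under 6.8 follow-up ends. The 3-month values stand, and there are no 6- or 12-month values. A pre-surgery score may exist, but 7.2 does not use it.
- Under 8.0, if the discontinuation is attributed to lack of effectiveness, follow-up continues where possible. A 12-month score would then be measured after surgery, and nothing in 7.2 stops it entering as a change due to AMDC.

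The two sections give different data for the same patient, and 7.2 lacks a rule under either.

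**Possible size.** The documents contain no figure to reproduce: the sample size of 50 is given without effect size, SD or dropout, and there is no re-treatment rate. What follows is illustrative.

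Inputs: 50 treated patients (6.1, 6.6); k re-treated before the visit (assumed 2, 5, 10 or 15); w = k/50; no other missing data (assumed).

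1. *Zero change in re-treated patients (assumed).* If the other 50 − k have mean change m, the available-case mean is m and the all-treated mean is m(50 − k)/50. The ratio is 50/(50 − k). For example, with an assumed Wexner change of −5.0 in 40 patients, the all-treated mean is (40 × −5.0 + 10 × 0)/50 = −4.0, and 5.0/4.0 = 1.25.
2. *Upper bound.* If changes are normal and the k worst are exactly the ones lost, the bias in SD units is φ(z_w)/(1 − w), where z_w is the w-quantile of the standard normal. For comparison, the 95% confidence half-width of a mean with n = 50 − k is t(0.975, n − 1)/√n SD.
3. *Proportion improved.* Assume about half of the remaining patients improve, then count the k re-treated patients as not improved.

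| k | n left | 50/(50 − k) | Upper-bound bias (SD) | CI half-width (SD) | Improved, available | Improved, all treated |
|---|---|---|---|---|---|---|
| 2 | 48 | 1.04 | 0.090 | 0.290 | 24/48 = 50% | 24/50 = 48% |
| 5 | 45 | 1.11 | 0.195 | 0.300 | 22/45 = 49% | 22/50 = 44% |
| 10 | 40 | 1.25 | 0.350 | 0.320 | 20/40 = 50% | 20/50 = 40% |
| 15 | 35 | 1.43 | 0.497 | 0.344 | 17/35 = 49% | 17/50 = 34% |

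At k = 10 the exact (Clopper-Pearson) 95% intervals are 34% to 66% for 20/40 and 26% to 55% for 20/50.

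**Sensitivity to the zero-change assumption.** If the 10 re-treated patients had half the benefit of the others, the all-treated mean would be (40m + 10 × 0.5m)/50 = 0.9m and the ratio 1/0.9 = 1.11 instead of 1.25. If they had the same benefit as the others, there would be no bias. If they had worsened, the ratio would exceed 1.25.

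**The case against.** The case against has several sound parts.

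- A reader might infer that the later summaries contain only patients in whom AMDC worked. The documents do not support that. The trigger in 6.8 is receiving another treatment, not needing one, so a non-responder who has no other procedure stays in and is measured at 6 and 12 months.
- A reader might also infer that 7.2 prescribes a completers-only or available-case analysis. It does not; it is silent. The bias is conditional on available values being summarized, which is the natural default but is not stated.
- Section 6.8 does try to obtain a score before the other procedure, and 8.0 points towards continued follow-up. Both could limit the loss. However, the first is only an attempt with no defined use, and the second applies where possible and contradicts the specific rule in 6.8.
- The trigger is not expressly limited to incontinence treatment, and it is unclear whether a change of medication counts. Not every withdrawal under 6.8 need be an AMDC failure.
- Efficacy is secondary and descriptive, and 6.9 disclaims definitive conclusions. No formal test is distorted. With 2 to 5 patients re-treated, even the upper-bound bias is below the confidence half-width.

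These arguments limit the strength of the point but do not remove it. The statement in 9.0 that included cases stay in the analysed population does not answer it either, because it concerns centres that stop enrolling after disagreeing with a monitoring-board decision.

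**Conclusion.** The point holds in a limited form. Sections 6.8 and 8.0 conflict on follow-up after another treatment, and neither 2.2 nor 7.2 says how these patients count. If available values are summarized, the direction is likely to favour AMDC. This applies to diary, Wexner and FIQL at visits after re-treatment, and to manometry and ultrasound at 12 months only.

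The size cannot be determined from the documents. Under zero change in re-treated patients and otherwise complete data, the overstatement is 4% for 2 of 50, 11% for 5 and 25% for 10. Only in the worst case, and at about 10 re-treated, does the bias (0.350 SD) exceed the half-width of the confidence interval (0.320 SD). The consequence is for interpretation and for what is carried into a larger trial, so the change is advisable but not critical.

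**What to change.** Reconcile 6.8 with 8.0 on follow-up and data collection after another treatment. Then add to 7.2:

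(a) The number, percentage and timing of treated patients who received another incontinence treatment by 3, 6 and 12 months, with a definition of which treatments count (including whether medication changes do). Add an improved/not-improved table over all treated patients that counts them as not improved from that date. The plan has no definition of improvement, so one must be fixed in advance.

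(b) Beside the available-case change from baseline, an all-treated summary that uses the pre-procedure score where one was obtained and no change from baseline otherwise. Label it a sensitivity analysis and state how many values were filled in. It should not replace the observed summary: single imputation treats assumed values as data in the confidence intervals, and a full 28-day diary or a manometry reading may often be unavailable before the procedure.

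(c) If data are collected after the other treatment, list them separately and do not pool them as AMDC effect.

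The cost is analysis wording and extra table rows, with no new visits or procedures. The exit form already requires the reason for withdrawal, but the examples in 6.8 do not list re-treatment as a category, so it may need to be coded from the explanation. The efficacy figures will probably look somewhat less favourable.
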